
Objective

Primary objective:

1. To determine the effect of flushing after HIPEC on tissue platinum exposure

Secondary objectives:

1. To explore the effect of flushing after HIPEC on wound exudate platinum concentration
2. To explore the effect of flushing after HIPEC on systemic exposure of total and unbound platinum

3. To explore the relation between the platinum concentration in instillate on tissue platinum exposure
4. To explore the relation between the platinum concentration in instillate on systemic exposure of total and unbound platinum exposure
5. To explore the effect of the degree of cytoreduction on systemic total and unbound platinum exposure

Study design

Single-centre, prospective, open, pharmacokinetic (PK) cohort study.

Study population

Twenty patients with peritoneal carcinomatosis as a result of intra-abdominal cancers who are already planned for HIPEC treatment with oxaliplatin as part of routine clinical care will be included in the study.

Intervention

The first 10 patients will undergo HIPEC procedure with flushing afterwards (the current practice by Radboudumc), followed by 10 patients who will be treated with HIPEC without flushing afterwards (new Radboudumc protocol that will be implemented in the beginning of 2018). Peritoneal fluid, peritoneal tissue, blood and wound exudate samples will be collected in all patients on prespecified time points during and after the HIPEC procedure.

Main study parameters/endpoints:

The main study parameter is the change in tissue platinum exposure before and after flushing. Tissue platinum exposure is expressed in concentration platinum per milligram tissue (ng/mg).

Nature and extent of the burden and risks associated with participation, benefit and group relatedness

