Two 5-cm diameter non-tumour peritoneal tissue samples will be taken from all patients that underwent HIPEC with flushing afterwards. The first sample will be taken immediately after the instillate solution is evacuated from the abdominal cavity. The second sample will be taken immediately after flushing. In the group of patients receiving HIPEC without flushing one 5-cm diameter non-tumour peritoneal tissue sample will be taken immediately after the instillate solution is evacuated from the abdominal cavity. Immediately after resection, all tissue samples will be touched to filter paper in order to remove excess surface fluid. The processing of the tissue will be performed according to the method described by Elias et al. The concentration in non-tumour peritoneal bathed tissue is a good reflection of tumour bathed tissue (9).

Peritoneal fluid samples

To determine the decrease in concentration of unbound platinum concentrations in the heated peritoneal instillate three different 5ml fluid samples will be collected at the following time points: 5 minutes after the start of the HIPEC procedure, 15 minutes after the start of the procedure and at the end of the HIPEC procedure. Based on the measurements in these samples it is possible to follow the decrease of unbound platinum concentrations in the heated peritoneal instillate. An additional 5ml fluid sample will be taken from the sodium chloride 0.9% flush solution at the end of flushing, to determine unbound platinum concentration in the flushing fluid.

Blood samples

A total of thirteen 10ml heparinised blood samples will be collected from each patient. Each sample will be centrifuged within 10 minutes after collection for 5 minutes (1,000 g, 4°C) to separate plasma. Unbound platinum will be obtained by centrifuging the plasma fraction through a 30 kDa cut-off ultrafiltrate filter for 15 minutes (1,000 g, 20°C). Unbound platinum from plasma is performed as soon as possible after blood collection, to prevent a decrease of Pt levels due to progressive *ex vivo* binding of Pt to plasma proteins and erythrocytes. The unbound platinum will be stored at -20°C until analysis. The first three blood samples will be taken at 10, 20 and 30 minutes after the start of HIPEC. The other ten samples will be taken at $\frac{1}{4}$, $\frac{1}{2}$, 1, 2, 4, 12, 24, 36, 48 and 72 hours after completion of the HIPEC procedure.

[figure not shown]

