8.2 Randomisation, blinding and treatment allocation

As this is an open label study, blinding procedures are not applicable. A total of 20 patients will be included in the study. The first 10 included patients belong to the *flushing* group and the last 10 included patients belong to the *non-flushing* group.

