10.2.2 Secondary study parameter(s)

- To explore the difference in platinum wound exudate concentration between patients with and without flushing after completion of HIPEC: mean wound exudate concentrations will be calculated for both groups (flushing vs. non-flushing). An independent t-test will be performed to explore differences.
- To explore, quantify and describe the effect of flushing after HIPEC on systemic exposure of oxaliplatin: The mean AUCs of unbound platinum will be calculated. AUCs of flushing vs. no flushing will be compared by performing an independent t-test
- To explore, quantify and describe the effect of platinum concentration in instillate on tissue platinum exposure: Regression analysis will be performed to model the relationship
- To explore, quantify and describe the effect of the degree of cytoreduction on systemic unbound platinum exposure: Regression analysis will be performed to model the relationship
- To explore, quantify and describe the effect of platinum concentration in instillate on systemic unbound platinum exposure: Regression analysis will be performed to model the relationship

PK parameters for unbound platinum (AUC_{0-72h} , C_{max} and t_{max}) will be calculated by non-compartmental analysis. After finalizing the study the data will additionally be analyzed by Nonlinear mixed effect modeling to estimate the PK parameters for the population and the individual patients.

Based on the individual concentration-time data, the following PK parameters will be determined (non-compartmental analysis).

AUC_{0-72h} : the area under the unbound platinum concentration-time curve calculated (linear trapezoidal method) until the last measurable platinum concentration.

C_{max} : the maximum unbound platinum drug concentration

t_{max} : the time to reach maximum unbound platinum drug concentration.

Individual and mean unbound platinum concentrations will be presented. Overlay presentations will be given to illustrate intersubject variability. Descriptive statistics will be used to calculate the unbound platinum concentration at each sampling time.

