APPENDIX 3: Study procedures overview

Procedure	Flushing group				
	Screening	Time relative to the day of surgery			
	Day -14 until day 0	Day 0	Day 1	Day 2	Day 3
Written informed consent	X				
Inclusion/exclusion criteria	X				
Anamnesis/medical history	X				
Demography	X				
Concomitant Medications	X				
Laboratory clinical chemistry	X				
Cytoreduction and HIPEC with flushing afterwards ¹		X			
Blood PK sampling ²		X	X	X	X
Peritoneal PK sampling ³		X			
Tissue collection ⁴		X			
Wound exudates sampling ⁵		X	X	X	X

¹ flushing is performed with 2L/m² of sodium chloride 0.9% during 5 minutes

² blood samples (timepoints relative to the start of HIPEC): 10min, 20min, 30min, 45min, 1h, 1½ h, 2h, 4h, 12h, 24h, 36h, 48h, 72h.

³ peritoneal samples (timepoints relative to the start of HIPEC): oxaliplatin solution: 5min, 15min, 30min; flushing solution: 45min.

⁴ tissue samples of peritoneum: pre- and post-flushing

⁵ wound exudate samples will be taken each time a drain bottle is changes. Sampling continues until the drain is removed or until day 3 post-HIPEC has been reached.

Procedure	Non-flushing group				
	Screening	Time relative to the day of surgery			
	Day -14 until day 0	Day 0	Day 1	Day 2	Day 3
Written informed consent	X				
Inclusion/exclusion criteria	X				
Anamnesis/medical history	X				
Demography	X				
Concomitant Medications	X				
Laboratory clinical chemistry	X				
Cytoreduction and HIPEC without flushing afterwards ¹		X			
Blood PK sampling ²		X	X	X	X
Peritoneal PK sampling ³		X			
Tissue collection ⁴		X			
Wound exudates sampling ⁵		X	X	X	X

¹ no additional flushing is performed

² blood samples (timepoints relative to the start of HIPEC): 10min, 20min, 30min, 45min, 1h, 1½ h, 2h, 4h, 12h, 24h, 36h, 48h, 72h.

³ peritoneal samples (timepoints relative to the start of HIPEC): oxaliplatin solution: 5min, 15min, 30min

⁴ tissue sample of peritoneum after evacuation of oxaliplatin-solution

⁵ wound exudate samples will be taken each time a drain bottle is changes. Sampling continues until the drain is removed or until day 3 post-HIPEC has been reached.

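### Unbound platinum AUC gets three separate single-factor analyses in consecutive, non-randomised groups; one joint model would be more precise and guard against bias from unequal groups

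*Protocol*

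**What the plan says.** **AUC analyses.** For the flushing comparison, Section 10.2.2 states: "AUCs of flushing vs. no flushing will be compared by performing an independent t-test". It then lists three regressions: tissue platinum on instillate concentration, AUC on degree of cytoreduction, and AUC on instillate concentration. All three share one sentence, "Regression analysis will be performed to model the relationship". No model form, covariate or analysis set is given. Nonlinear mixed-effects modelling is planned afterwards to estimate PK parameters, also without named covariates.

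**Allocation.** Section 8.2: "A total of 20 patients will be included in the study". Groups are formed by order of inclusion; the Summary says "The first 10 patients will undergo HIPEC procedure with flushing afterwards", and the next 10 are not flushed.

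**Tissue samples.** Section 3 gives flushed patients two samples. Of the first it says "The first sample will be taken immediately after the instillate solution is evacuated from the abdominal cavity", and of the other "The second sample will be taken immediately after flushing". Unflushed patients give one sample. Section 3 and Appendix 3 place it after evacuation ("tissue sample of peritoneum after evacuation of oxaliplatin-solution"), but the Summary and Section 11.4 place it just before the abdomen is closed. Section 10.2.2 does not say which flushed sample enters the tissue regression.

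**Status.** Section 4.4 calls all secondary objectives exploratory and gives no sample size for them.

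**The concern.** The same outcome in the same 20 patients is taken apart one factor at a time, and no analysis is stated to allow for the other factors. Flushing is the factor the study is built around, and Section 10.2.2 itself treats it as a possible determinant of AUC. Section 3 uses PCI for the extent of disease. Section 8 of the methods does not randomise, so nothing protects against the two groups differing in instillate concentration or PCI, and Section 1 says concentration varies greatly with the volume of the abdominal cavity.

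Two things are at stake. If flushing matters and is left out, its effect goes into the residual and the slopes are less precise. If the groups also differ in a predictor that affects AUC, part of one effect is credited to another. That applies to the flushing t-test as well as to the slopes.

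**Working it through.** **The plan's own figure.** The only calculation in the protocol is the 10 patients for the paired primary comparison. On the log scale, with a 25% fall, within-patient CV 20% and SD of the difference √(2·ln 1.04) = 0.280, a one-sided 5% paired t-test on 10 patients has 91.1% power. The figure reproduces, but it does not bear on this point. The protocol gives no figure for the regressions.

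**Inputs.** From the protocol: 10 + 10 patients, allocation by order. Assumed, because the protocol gives none: flushing effect δ, slope, group difference in the predictor s (in within-group SDs) and residual spread. Tests are two-sided at 5%, with 20,000 simulated trials per setting. Balanced means no systematic group difference in the predictor.

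**Step 1: precision, balanced predictor.** In residual-SD units, leaving out flushing inflates the residual variance by about 1 + δ²/4: 1.06 at δ = 0.5, 1.25 at 1 and 2.0 at 2. With a true slope of 0.7, the mean slope is 0.70 in every row with or without the term, so there is no bias. Power for the slope is:

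| Flushing effect (SD) | Without term | With term |
|---|---|---|
| 0 | 79% | 77% |
| 0.5 | 77% | 77% |
| 1 | 70% | 77% |
| 1.5 | 61% | 77% |
| 2 | 51% | 77% |

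**Step 2: bias of the slope.** For equal groups and a predictor with unit within-group SD, the large-sample bias is (δ·s/4)/(1 + s²/4). With δ = −1 and s = +0.5 this is −0.125/1.0625 = −0.12. Simulated mean slopes against a true 0.70 are 0.57 if the predictor is higher in the flushed group and 0.82 if it is lower. With the term the slope is 0.70 in both cases. With a true slope of zero and a difference of half an SD, the test without the term rejects about 7% of the time at δ = −1 and about 12% at δ = −2, against 5% with the term.

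**Step 3: the same on an AUC scale.** Assume residual CV 30% (log SD √ln 1.09 = 0.294), SD of log concentration 0.25, true slope 1, and a 25% fall from flushing (ln 0.75 = −0.288, or 0.98 residual SD).
- Balanced: power for the slope is 84% without the term and 88 to 89% with it.
- Half-SD difference: slope 0.86 without the term if concentration is higher in the flushed group, 1.14 if lower, and 1.00 with the term either way.

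**Step 4: the flushing comparison, same inputs, log scale.** Bias of the unadjusted difference = slope × group difference in the predictor = 1 × 0.5 × 0.25 = 0.125. If concentration is higher in the flushed group, the expected difference is −0.288 + 0.125 = −0.163, an apparent fall of 1 − e^(−0.163) = 15% instead of 25%. If lower, it is −0.413, an apparent fall of 34%. When balanced there is no bias, but adjusting for concentration raises power for the flushing effect from 35% to about 52 to 53%.

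**Step 5: how likely is such a difference?** The standard error of a difference between two means of 10, in SD units, is √(2/10) = 0.447, and 0.5/0.447 = 1.12. A difference of at least half an SD in either direction therefore arises by chance about 26% of the time, before any time trend.

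**Step 6: cost of the term if flushing does nothing.** Power for the slope falls by about 2 points when balanced (79% to 77%; 90% to 89% on the Step 3 inputs is nearer 1 to 2). With a half-SD difference it falls by 3 points on the Step 3 inputs (92% to 89%) and by about 5 with slope 0.7 (82% to 77%).

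**Step 7: tissue regression.** On the timing in Section 3 and Appendix 3, the unflushed sample and the first flushed sample are both taken after evacuation and before any flush, so flushing cannot affect either. It enters only if the post-flush sample is used, or if the unflushed sample is taken at closure as the Summary and Section 11.4 say.

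**The case against.** The strongest objection is that the protocol is silent rather than wrong. It does not say that all 20 patients are pooled without a flushing term, and it does not exclude adjustment. A covariate list for an exploratory regression often sits in the statistical analysis plan, which is not at hand. This stands as a limit: a reader might infer that the protocol commits to an unadjusted pooled fit, but the text does not support that. What remains is that Section 10.2.2 does set out a method, three one-factor analyses of one outcome, and a single model on data already collected does the same job better.

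Two further objections stand in part. The protocol reports a lack of knowledge about the effect of flushing, and flushing comes after the perfusion, so a large effect on AUC cannot be presumed. No passage supports a halving of AUC, for example, and the larger losses in Step 1 are illustrations only. Second, power is a secondary yardstick for objectives declared exploratory. But Section 10.2.2 also aims to quantify these effects, and a confounded estimate misquantifies them whatever its status.

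**Conclusion.** The point holds as an improvement to the analysis, of low severity. If flushing changes AUC, leaving it out of a regression on all 20 patients costs precision: nothing visible at 0.5 residual SD, about 4 to 7 power points near 1 SD, and 26 at 2 SD. Bias needs a second condition, a group difference in the predictor. The same difference biases the unadjusted flushing comparison when the predictor affects AUC.

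Three stronger readings are tempting and not supported. A flushing effect alone does not bias a slope. Bias does not always weaken it; it can equally inflate it. And the tissue regression is not affected in the same way as the two AUC regressions: there the defect is that the sample is not named and its time is stated in two ways.

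Every magnitude depends on assumed effects, spreads and group differences; none is a protocol figure.

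**What to change.** In Section 10.2.2, replace the three AUC analyses with one linear model of log AUC on flushing group, log instillate concentration and PCI, and report all three effects with confidence intervals. State which instillate sample supplies the concentration. Concentration and PCI are both measured before flushing, so adjusting for them does not remove any of its effect. PCI is the workable measure of extent, because keeping only CC-0 patients makes the CC score constant.

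For the tissue regression, specify the post-evacuation, pre-flush sample in the flushing group. Reconcile Section 3 and Appendix 3 with the Summary and Section 11.4 on when the unflushed sample is taken.

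The cost is wording, with no extra patients or samples. Residual degrees of freedom fall from 18 to 17 with one added term, or to 16 with all three factors. The power cost if flushing has no effect is the few points in Step 6.

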Total unbound platinum concentrations will be measured. The individual AUCs are calculated with a trapezoidal approach.

Wound exudate samples

After the HIPEC procedure in the majority of patients one or more drains will be placed. The wound exudate is collected in drainage bottles. Each bottle is changed after 24 hours. This is the moment that personnel can be exposed to contaminated wound exudate. Each drain will produce around 100ml on the first day. The total volume of wound exudate per drain will be measured. A 5 ml sample of wound exudate will be collected from every drain bottle to determine total and unbound platinum concentration. Platinum concentrations will be measured with AAS in The Cancer biology laboratory, Institut Universitaire du Cancer de Toulouse (IUCT) Oncopole.

Duration and setting of the study

The study takes place at Radboud University Medical Centre in Nijmegen, the Netherlands. The study is expected to start in November 2017 and is expected to be completed within 1 year after study initiation.

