8.3 Study procedures

After the patient has given written informed consent, each patient will undergo an enrolment medical examination in the 14 days prior to the HIPEC procedure. In table 1 a summary is listed of the parameters that should be collected prior to the HIPEC procedure.

Table 1: summary of study procedures during the study

Procedure	Baseline	Day 1	Day 2	Day 3
Time window	-14d			
Informed consent form	X			
Demographics ^a	X			
Medical history/progress notes	X			
Concomitant medication and herbs	X			
Treatment toxicity/ AEs (CTCAE v4.0)				
Routine laboratory tests ^b	X	X	X	X
Pharmacokinetics ^c		X	X	X
Tissue sampling		X		
Exudate sampling		X	X	X
Electrocardiogram	X	X		

- a. Date of birth, gender, ethnicity, body weight, body height and current smoking status.
- b. Including Karnofsky performance status (see APPENDIX 2).
- c. Oxaliplatin administration at the hospital, blood samples at 10, 20 and 30 minutes after the start of HIPEC and at 1/4, 1/2, 1, 2, 4, 12, 24, 36, 48 and 72 hours after completion of the HIPEC procedure.

The study procedures overview is given in APPENDIX 3. The study procedures overview displays in detail the days and time-points for PK blood sampling, collection of peritoneal fluid samples, resection of peritoneal tissue and collection of wound exudate. Patients have to come to the hospital at screening and the day prior to the day of surgery. After surgery patients stay for approximately one to two days on the intensive care unit. After the study ended the effect of the cytoreduction and HIPEC procedure will be evaluated according to standard treatment care.

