8.5 Replacement of individual subjects after withdrawal

Patients who do not achieve a cytoreduction score of CC-0 will be excluded from the study and replaced by another patient. Patients will be replaced if only <50% of the required pharmacokinetic samples can be collected for any reason. A maximum number of 10 patients will be replaced.

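### Unbound-platinum AUC is fixed to the linear trapezoidal rule on a widely spaced declining curve; interpolation error is upward and depends on which samples a patient has, and linear-up/log-down would reduce it at almost no cost

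*Protocol*

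**What the plan says.** Section 10.2.2 of the protocol names the rule. AUC0-72h for unbound platinum is "calculated (linear trapezoidal method) until the last measurable platinum concentration". The blood-sample part of section 3 is less specific: "The individual AUCs are calculated with a trapezoidal approach".

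The same part of section 3 sets the schedule. "A total of thirteen 10ml heparinised blood samples will be collected from each patient". "The first three blood samples will be taken at 10, 20 and 30 minutes after the start of HIPEC", and the other ten follow at 1/4, 1/2, 1, 2, 4, 12, "24, 36, 48 and 72 hours after completion of the HIPEC procedure". Appendix 3 uses a different time origin: "blood samples (timepoints relative to the start of HIPEC): 10min, 20min, 30min, 45min, 1h, 1½ h, 2h, 4h, 12h, 24h, 36h, 48h, 72h".

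Section 8.5 sets the tolerance for missing samples: "Patients will be replaced if only <50% of the required pharmacokinetic samples can be collected for any reason". It does not say which time points must be present.

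Systemic unbound-platinum exposure is the outcome in three of the five secondary analyses in 10.2.2. These are the t-test of flushing against no flushing, and the regressions on degree of cytoreduction and on instillate concentration. Section 4.4 calls all secondary objectives exploratory. Section 10.2.2 adds a nonlinear mixed-effects analysis after the study, but does not say that the t-test or the regressions use its output.

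**The concern.** If platinum peaks near the end of the 30-minute perfusion, nearly all the sampled period lies on the falling part of the curve. The linear rule joins two points with a chord, and the chord over a convex decline lies above the curve. The excess grows with the fold-fall across the gap, so it is largest where sampling is sparse and larger again where a sample is missing.

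With complete sampling, every patient carries a similar upward error and comparisons between patients change little. Once patients miss different samples, the error becomes patient-specific. It then adds noise to a t-test with 10 patients per group and to regressions on at most 20, and it could shift a group in which more intermediate samples were lost. A rule that uses the same data with less error is available.

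**Working it through.** **1. Share of the schedule after evacuation (section 3).** Thirteen samples plus time zero make 13 intervals. Three end during the 30-minute perfusion and 10 follow it. With the last sample 72 h after completion, the span is 72.5 h from the start, and 72 / 72.5 = 99.3% of it lies after the end of HIPEC. The gaps after the 4 h sample are 8, 12, 12, 12 and 24 h.

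**2. Missing samples tolerated (section 8.5).** Half of 13 is 6.5. Counting blood samples, a patient with 7 of 13 is kept and 6 of 13 (46%) may be missing, wherever they lie.

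**3. One interval.** For an exponential decline by a factor F across a gap, linear area / true area = [(F + 1)/2] × ln F / (F − 1). The half-lives below are assumptions.

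| Half-life | 4–12 h | 4–24 h (12 h sample missing) |
|---|---|---|
| 4 h | F = 4: 2.5 × 1.386 / 3 = 1.155, +15.5% | F = 32: 16.5 × 3.466 / 31 = 1.845, +84.5% |
| 8 h | F = 2: 1.5 × 0.693 / 1 = 1.040, +4.0% | F = 5.66: +23.9% |
| 24 h | F = 1.26: +0.4% | F = 1.78: +2.8% |

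These are errors in one segment, not in total AUC.

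**4. Total AUC.** Two sets of assumed kinetics were run on the section 3 times. Each takes a 30-minute peritoneal input followed by biexponential decline, and compares each rule with the finely integrated area from 0 to 72.5 h.

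- Set A: fast half-life 0.25–1 h, slow half-life 6–48 h, fast-phase weight 70–95%, absorption half-life 0.5 h, 0 or 10% residual input after HIPEC.
- Set B: first half-life 0.5–3 h, second 12–24 h, slow fraction 2–10%, absorption half-life 0.6 h.

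| Samples | Set | Linear | Linear-up/log-down |
|---|---|---|---|
| All 13 | A | +0.4 to +11.7% (median +3.3%) | 0.0 to +4.0% (median +0.7%) |
| All 13 | B | +2 to +14% | +1 to +4% |
| 12 h missing | A | +0.6 to +33.9% | 0.0 to +11.8% |
| 12 h missing | B | +3 to +52% | +1 to about +17% |

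A further run over assumed half-lives reached +14% and +55% for the linear rule, against +4% and +17% for linear-up/log-down. The upper ends with the 12 h sample missing are therefore about 35 to 55% against 12 to 17%.

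**5. Patterns that go the other way (set A).**

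| Missing | Linear | Linear-up/log-down |
|---|---|---|
| 48 h and 72 h | −36 to +11% | −36 to +3% |
| Last six | −93 to −31% | −93 to −32% |
| 20 min, 30 min and 1/4 h | −8.0 to +4.7% | −13.4 to −0.2% |

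Across all 1,716 ways of keeping 7 of 13 samples, 2% to 51% of patterns underestimate AUC under the linear rule, depending on the assumed kinetics. Late losses truncate the area, and the log rule makes almost no difference to that. When the samples around the peak are lost, the log rule lies slightly lower than the linear one.

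**6. Effect on a group mean.** One patient in a group of 10 with an error of +40%, and otherwise an average AUC, moves the group mean by 40 / 10 = 4%.

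**The case against.** The linear trapezoid is a recognised non-compartmental method, and fixing it in advance is better than leaving it open. The wording in section 3 is compatible with 10.2.2. With complete sampling the error is largely common to both groups, so the ratio of AUCs hardly moves, and all three AUC analyses are comparisons or regressions. The analyses are exploratory and unpowered. Samples come from a central venous catheter already placed for routine care, and patients spend about one to two days in intensive care, so nothing in the protocol suggests that the 12 h draw would be missed often, or more in one group. The planned mixed-effects analysis can handle incomplete profiles. All of this stands, and it is why the point is minor.

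Two stronger readings are tempting, and the protocol supports neither. A reader might infer that AUC will be overestimated whatever is missing. That fails, because the area ends at the last measurable concentration and lost late or peak samples can pull it down. A reader might also infer that the log rule settles the missing-sample problem. It reduces interpolation error on the decline, but leaves truncation untouched and does not restore a missed peak.

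The objection does not remove the remaining point. The mixed-effects analysis is only a partial safeguard, since the t-test and regressions are not tied to it. For gaps on the decline, linear-up/log-down has the smaller error in every case in step 4, from the same samples.

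**Conclusion.** The point holds in a limited form. Section 10.2.2 fixes a rule whose interpolation error between retained samples on the decline is upward, and grows when an intermediate sample is missing. Under assumed kinetics the error in total AUC is roughly 0.5 to 14% with full sampling and up to about 35 to 55% without the 12 h sample. Linear-up/log-down gives up to about 4% and 12 to 17%. No half-life is given in the protocol, so these sizes rest wholly on the assumed ranges and on a peak near the end of perfusion.

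With complete data the gain is in absolute AUC rather than in the group comparison. A separate weakness is that the area stops at the last measurable value but carries the label AUC0-72h, so patients with missing terminal samples are compared over different windows. This is worth correcting as an inexpensive improvement. It does not threaten the primary objective.

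**What to change.** - **Section 10.2.2:** replace the linear trapezoidal rule with the linear rule while concentrations rise and the logarithmic rule while they decline, using actual sampling times. The linear result can be kept as a sensitivity analysis.
- **Section 3:** align the general reference to a trapezoidal approach with that wording.
- **Truncation:** compute AUC over a window common to all compared patients, or take the AUC of patients with missing terminal samples from the planned mixed-effects model, and say which in 10.2.2.
- **Sampling times:** section 3 and Table 1 in section 8.3 count the ten later samples from completion of HIPEC, and Appendix 3 counts all samples from the start. The two must be reconciled so that actual times have one origin.

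The cost is a setting in the non-compartmental software and a few sentences. A common window discards some late data if the shortest profile is short; the model-based option avoids this but relies on the model's fit. No sample or patient procedure need be added.
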